## Statistical analysis

We analyzed outcomes depending on whether the patient belonged to the ERAS program or the retrospective standard cohort. The discrete and continuous variables were described as number and percentage and median (interquartile range [IQR]) and their differences analyzed using the Pearson test or the Wilcoxon rank-sum tests. Subsequently, according to the adherence rate to ERAS items (regardless of whether the patients belonged to the ERAS or the retrospective standard cohort), We performed a multivariate logistic analysis to study the association of complication rates, readmission or pain with ERAS adherence, clinical and demographic data, presenting the results in forest plots as odds ratio with 95% confidence interval. Similarly, we used Cox regression for multivariate analysis of length of stay, presenting the results in forest plot as hazard ratio with 95% confidence interval. To avoid errors by multiple comparisons, we calculated the respective q-value for each p-value to maintain a false discovery rate below 5%. We considered comparisons in which p-value and q-value were below .05 as being statistically significant.

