## RESULTS

No patient declined inclusion in the study. The demographic characteristics and comorbidities of the patients are shown in Table 1. The two cohorts were not totally homogeneous, with a higher number of patients with hypertension in the standard cohort [26 (52%) vs ERAS 15 (30%),  $p = 0.03$ ] and chronic obstructive pulmonary disease [12 (24%) vs ERAS 4 (8%),  $p = 0.02$ ]. Although the number of patients with ASA class  $> 2$  was higher in the standard group [26 (52%) vs ERAS 15 (30%)], we found no difference between the cohorts in Charlson's comorbidity index. We included these three items, along with age and sex in the subsequent multivariate analyses.

Data on ERAS adherence and compliance for each of the protocol items are shown in Table 2. Adherence to the ERAS protocol was significantly higher in the prospective than in the retrospective cohort [Median: Standard 0.29 (0.14-0.43) vs ERAS 0.71 (0.57-0.82),  $p < 0.001$ ]. The VATS approach was greater in the ERAS group [29 (58%) vs Standard 11 (22%),  $p < 0.001$ ], and the number of patients who ambulated on the first postoperative day [40 (80%) vs Standard 0 (0%),  $p < 0.001$ ], but no difference was found in the use of regional analgesia. Also, the times to oral intake and removal of the urethral catheter were lower in the ERAS group [Median (h): Standard 24 (24-24) vs ERAS (6-7.5), and Standard 48 (24-48) vs ERAS 19 (6-24), respectively].

The primary and secondary results are shown in Table 3. We found no difference between the two groups in either surgical complications [Standard 18 (36%) vs 12 (24%),  $p = 0.19$ ], non-surgical complications [Standard 21 (42%) vs 12 (24%),  $p = 0.06$ ] or length of stay [Median (days): Standard 4 (3-6) vs 4 (3-5),  $p = 0.19$ ], and the ERAS group was significantly lower only in its readmission rate [Standard 15 (30%) vs 6 (12%),  $p = 0.03$ ]. No deaths were recorded in the ERAS group, compared to two deaths in the retrospective cohort.

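### The ERAS-versus-standard comparison is made only with unadjusted tests despite recorded baseline imbalance; the adjusted models estimate the effect of adherence, not of the programme

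*SAP*

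**What the plan says.** The Protocol (Study design and participants) sets a prospective ERAS cohort against a retrospective cohort from before the programme. Procedures gives 50 patients from 2018-2019 and the last 50 from 2016.

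The SAP (Statistical analysis) specifies two separate analyses:

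- By cohort: "We analyzed outcomes depending on whether the patient belonged to the ERAS program or the retrospective standard cohort", with "their differences analyzed using the Pearson test or the Wilcoxon rank-sum tests".
- By adherence: multivariable logistic models (complications, readmission, pain) and a Cox model (length of stay), fitted to all patients by adherence rate, "regardless of whether the patients belonged to the ERAS or the retrospective standard cohort".

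The Results section then reports:

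- Imbalance: "The two cohorts were not totally homogeneous, with a higher number of patients with hypertension in the standard cohort" (52% vs 30%), with COPD 24% vs 8% and ASA class above 2 52% vs 30%. For Charlson's index, "we found no difference between the cohorts in" it.
- Covariates: "We included these three items, along with age and sex in the subsequent multivariate analyses".
- Adherence: "Adherence to the ERAS protocol was significantly higher in the prospective than in the retrospective cohort", with medians 0.29 and 0.71.
- Outcomes by cohort: surgical complications 36% vs 24%, non-surgical complications 42% vs 24%, and length of stay, all without a significant difference; "the ERAS group was significantly lower only in its readmission rate" (30% vs 12%).

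Every multivariable estimate quoted in the text is for adherence or for an analgesic technique. No odds or hazard ratio for cohort appears.

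**The concern.** The study asks what the programme did, and that question is answered by the cohort contrast. With no randomisation, imbalance in prognostic factors biases a crude contrast. The authors evidently judged the imbalance worth adjusting for, but they adjusted a different contrast.

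The adherence models cannot take its place, for two reasons. Adherence is a consequence of the programme, so it lies on the path from programme to outcome. The score also contains postoperative items, such as early walking and early chest tube removal, which the patient's course can itself affect. If a forest plot does contain a cohort term beside adherence, that term would be the part of the programme effect not passing through adherence, not the programme effect.

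All three recorded imbalances run the same way, with more comorbidity in the standard cohort, so the crude differences may flatter ERAS. At stake are the size and significance of the readmission result.

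**Working it through.** **1. The reported cohort p-values are crude.** An uncorrected Pearson test on the reported counts (50 per cohort) gives:

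| Outcome | Standard vs ERAS | Recomputed p | Stated p |
|---|---|---|---|
| Surgical complications | 18 vs 12 | 0.190 | 0.19 |
| Non-surgical complications | 21 vs 12 | 0.056 | 0.06 |
| Readmission | 15 vs 6 | 0.027 | 0.03 |

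**2. Readmission is close to the threshold.** The difference is 0.30 − 0.12 = 18.0 points. SE = √(0.30×0.70/50 + 0.12×0.88/50) = 7.94 points, so the Wald 95% CI is 18.0 ± 1.96×7.94 = 2.4 to 33.6. The Newcombe interval is 1.9 to 33.2 and Fisher's p is 0.048. For surgical complications the difference is 12.0 points (CI −5.8 to 29.8).

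**3. Adherence odds ratios are on another scale.** If they are per unit of a 0-1 rate (an assumption), the median gap of 0.71 − 0.29 = 0.42 gives 0.02^0.42 = 0.19 for surgical complications and 0.01^0.42 = 0.14 for readmission. The crude cohort odds ratios are 0.56 and 0.32. One set cannot be read as the adjusted version of the other.

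**4. How much of the 18 points the imbalance could create.** The documents give no covariate-outcome odds ratios, so a range is assumed, with COPD and ASA above 2 independent and no programme effect. The model is logit(risk) = a + log(OR)×COPD + log(OR)×ASA, with a solved so that the standard cohort's risk is 0.30.

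Example, OR 2 for both: a = −1.413, giving risks of 0.196 (neither factor), 0.327 (one) and 0.493 (both).

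- Standard cohort weights: 0.76×0.48 = 0.365 (neither), 0.510 (one), 0.24×0.52 = 0.125 (both). Mean risk 0.300.
- ERAS cohort weights: 0.92×0.70 = 0.644, 0.332, 0.08×0.30 = 0.024. Mean risk 0.2465.
- Spurious difference: 5.3 points.

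| Assumed OR | Both | COPD alone | ASA above 2 alone |
|---|---|---|---|
| 1.2 | 1.5 | 0.6 | 0.8 |
| 1.5 | 3.2 | 1.4 | 1.9 |
| 2 | 5.3 | 2.5 | 3.1 |
| 3 | 8.1 | 3.9 | 4.8 |

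Hypertension alone gives the same figures as ASA above 2, because the reported split (26 vs 15) is identical. If the covariates oppose each other (COPD 1.5, ASA above 2 0.67), the net is −0.4 points.

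**5. Tipping point.** With the SE held fixed, the lower Wald limit reaches zero at OR 1.36 for both covariates, 1.98 for COPD alone or 1.70 for ASA above 2 alone. With the Newcombe limit the values are 1.28, 1.73 and 1.53.

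A risk-ratio check agrees. The crude RR is 0.40 (0.17 to 0.95). For a single confounder with risk ratio 1.5, the bias factor for COPD is (0.08×0.5+1)/(0.24×0.5+1) = 0.929, which moves the RR to 0.43 with upper limit 1.02. For ASA above 2 it is 1.15/1.26 = 0.913, giving 0.44 with upper limit 1.04.

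**6. Direction.** If the observed risks are the true ones, the difference standardised over both cohorts is 16.9, 15.5, 13.7 or 11.2 points for ORs of 1.2, 1.5, 2 and 3. It shrinks but keeps its sign.

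**7. Simulation of the remedy.** 8,000 datasets per setting were drawn with the reported COPD and ASA counts, and with age and sex unrelated to cohort and outcome. Under no programme effect, the crude test falsely favoured ERAS in 3.2, 5.6, 8.2 and 13.5% of studies for the four ORs. The adjusted model in the fix did so in 2.2, 2.5, 2.4 and 2.3% (nominal 2.5%).

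**The case against.** The tables and forest plots are not in the available text, and the covariate list in the SAP is open-ended: analgesic technique appears in the models although it is not among the covariates named in the Results. A cohort term therefore cannot be ruled out. That stands as a limit on what can be seen, but a cohort coefficient beside adherence would still not be the programme effect.

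The consequence is also narrow. The primary comparison and two of the secondary ones are already reported as showing no difference, the imbalance is disclosed, and readmission is borderline even without confounding. Charlson's index did not differ, and the larger bias figures need both covariates to carry odds ratios of 2 to 3. All of this is fair. It confines the point to one secondary result and a range from trivial to moderate.

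Finally, adjustment costs power. With the observed risks true and no confounding, the chance of a significant readmission result falls from 62% to 55%. If confounding is real, with ORs of 1.5 to 3, it falls to about 41 to 25%, partly because the adjusted effect is smaller. A non-significant adjusted result would therefore not show that the programme has no effect. This is a reason to report the estimate and interval, not to leave the adjusted analysis out.

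**Conclusion.** The concern holds. In the readable text the programme contrast is unadjusted, and the recorded imbalance is handled only in models of a variable that the programme changes. The primary result would probably stay null and the direction of the readmission difference is not in doubt.

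The size and significance of the readmission difference are insecure: moderate covariate effects in the assumed direction would be enough to take the interval to zero. How much of the 18 points is spurious cannot be settled without patient data. The figures rest on assumed odds ratios and independent covariates. This should be fixed; it does not invalidate the study.

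**What to change.** Add one model each for surgical complications, non-surgical complications and readmission:

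- Firth logistic regression with corrected intercept; cohort as exposure; adherence left out; adjusted for age, sex, COPD and ASA above 2.
- Standardise over all 100 patients to a risk difference with a delta-method 95% CI.
- For length of stay, a Cox model with the same terms, stating how the two deaths in the standard cohort are handled.
- As sensitivity analyses, replace ASA above 2 with hypertension, then with Charlson's index. Replacing rather than adding keeps five parameters. First check the ASA and hypertension counts, since the reported figures are identical.
- Consider the same model for pain, and say whether the new models enter the q-value family.

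Report these beside the crude tests, labelled post hoc because the results are known. Base any statement about readmission on both the adjusted and the crude estimate. State that adjustment cannot remove the 2016 versus 2018-2019 difference, which coincides entirely with cohort.

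The cost is one extra model per outcome, the sensitivity runs and some wording. No new data are needed, because demographic and comorbidity data were collected for all patients. Events per parameter are low: 30/5 = 6.0 (surgical), 33/5 = 6.6 (non-surgical) and 21/5 = 4.2 (readmission). In the no-effect simulations the adjusted SE was 1% smaller to 3% larger than the crude SE; at the observed risks without confounding it was about 4% larger (8.22 vs 7.87). Coverage was 94.5 to 95.4%. The Firth estimate shrinks by about 1 point (mean 16.7 against a true 18.0). Real data, where age and sex may matter, could give a wider interval. Unmeasured confounding remains and must be stated.

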specialized in therapy against lung diseases taught patients pulmonary expansion exercises to be carried out until surgery was performed. Smoking cessation and nutritional screening of the patient were also part of this stage.

The patients underwent video-assisted thoracoscopic surgery (VATS), whenever possible, leaving a chest tube at the end of the surgery. All subjects received antibiotic and antithrombotic prophylaxis. Intraoperative management of patients was performed under general anaesthesia combined with regional techniques for pain control, avoiding the use of benzodiazepines and opioids. Those patients in whom thoracic epidural catheter was implemented during surgery continued its use through a patient-controlled analgesia system. Besides, a hot air system warmed the patients during surgery to maintain normothermia. Extubation was performed as soon as possible after the end of the surgery, and we encouraged early removal of the urinary catheter.

From the time of extubation, the patients began oral tolerance and respiratory physiotherapy exercises. Also, the patients were allowed to walk around early. The patients were discharged when they were free of complications, without severe pain, urinary catheter or chest tube.

Outcomes

The primary outcome was the number of patients with 30-day surgical complications. We defined air leakage, bleeding, infection, and reintervention as surgical complications. Secondary outcome included ERAS adherence, no-surgical complications, mortality, readmission, reintervention rates, pain (defined as any level of pain that prevents early ambulation) and hospital lenght of stay. To evaluate ERAS adherence, we defined seven items: VATS approach, regional analgesia, oral tolerance within 6 hours, urinary catheter removal within 24 hours, ambulation within 24 hours, respiratory physiotherapy within 24 hours and chest tube removal within 48 hours.

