Multivariate analyses are shown in Figures 1, 2 and 3. ERAS adherence was the only factor associated with a reduction in surgical complications [OR (95%CI) = 0.02 (0.00, 0.59),  $p = 0.03$ , Figure 1A], and postoperative pain [OR (95%CI) = 0.01 (0.00, 0.28),  $p = 0.01$ , Figure 2B]. It was also associated with a lower readmission rate [OR (95%CI) = 0.01 (0.00, 0.24),  $p = 0.007$ , Figure 2A] and an increased likelihood of discharge from the hospital [HR (95%CI) = 18.5 (4.39, 78.4),  $p < 0.001$ , Figure 3]. The thoracic epidural analgesia was the only factor that showed an association with lower rates of non-surgical complications [OR (95%CI) = 0.09 (0.01, 0.49),  $p = 0.008$ , Figure 1B]. It was also associated with lower rates of postoperative pain [OR (95%CI) = 0.16 (0.03, 0.86),  $p = 0.03$ , Figure 2A] and increased probability of discharge from the hospital [HR (95%CI) = 3.14 (1.39, 7.07),  $p = 0.006$ , Figure 3]. The intercostal blockade also increased the latter likelihood [HR (95%CI) = 7.55 (2.94, 19.3),  $p < 0.001$ , Figure 3].

No significant  $p$ -value was rejected after the calculation of  $q$ -value within the multiple comparability study.

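### Regional analgesia is counted inside the adherence score and also reported as separate technique terms beside it, without a stated reference; the logistic models also have few events per term

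*SAP*

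**What the plan says.** The protocol (Outcomes) sets out the score: "we defined seven items: VATS approach, regional analgesia, oral tolerance within 6 hours", followed by early catheter removal, walking, physiotherapy and chest-tube removal. The SAP (Statistical analysis) pools both cohorts for the adherence models, "regardless of whether the patients belonged to the ERAS or the retrospective standard cohort", and describes the logistic part as follows: "We performed a multivariate logistic analysis to study the association of complication rates, readmission or pain with ERAS adherence, clinical and demographic data". Length of stay is handled by Cox regression. All these results go into forest plots.

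The adjusters appear in the SAP's RESULTS: "We included these three items, along with age and sex in the subsequent multivariate analyses". The three items are hypertension, COPD and either ASA class or Charlson index; the sentence can be read either way. Analgesic technique is not named as a term in either place.

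RESULTS then reports techniques as factors in their own right. For non-surgical complications: "The thoracic epidural analgesia was the only factor that showed an association with lower rates of non-surgical complications". Epidural is also reported for pain and for discharge. For discharge: "The intercostal blockade also increased the latter likelihood". Adherence, epidural and block all cite Figure 3 for discharge, so they sit in one Cox model. On overall use, the text says only "but no difference was found in the use of regional analgesia".

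**The concern.** Any patient with an epidural or a block also scores the regional-analgesia item. If that item stayed in the score, a technique coefficient is estimated with total adherence held fixed. Against a patient with no regional technique, the comparison is then between someone who met the item through the technique and someone who met a different item instead. That is not the technique-versus-none contrast a reader will take from hazard ratios of 3.14 and 7.55. Without the reference category and the content of the fitted score, those figures cannot be interpreted with confidence.

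The second matter is sparsity in the logistic models. The crude comparison of surgical complications is null (36% vs 24%, p = 0.19), so the only positive statement on the primary outcome is the adherence odds ratio of 0.02 (0.00, 0.59): "ERAS adherence was the only factor associated with a reduction in surgical complications". With few events per term, maximum likelihood tends to exaggerate the size of such an estimate.

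**Working it through.** **Inputs (SAP, RESULTS).** Discharge HRs: adherence 18.5 (4.39, 78.4), epidural 3.14 (1.39, 7.07), block 7.55 (2.94, 19.3). Surgical adherence OR 0.02, upper limit 0.59. Events, standard + ERAS: surgical 18 + 12 = 30; non-surgical 21 + 12 = 33; readmission 15 + 6 = 21. The text gives no pain count.

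**Reproducing the printed figures.** Uncorrected Pearson tests on the counts give p = 0.190, 0.056 and 0.027, against 0.19, 0.06 and 0.03 in print. The geometric midpoints of the Cox intervals are 18.55, 3.13 and 7.53, in line with the printed HRs.

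**Which score is described.** 1/7, 2/7, 3/7, 4/7 and 5/7 are 0.14, 0.29, 0.43, 0.57 and 0.71, the printed values. The remaining 0.82 is an interpolated quartile, 5/7 + 0.75/7 = 0.82. The score as described therefore has seven items coded 0 to 1. Whether it entered the models unmodified is not stated.

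**Overlap.** Let S be the number of the other six items met and T = 1 for a regional technique, with reference none. The linear predictor is b(S + T)/7 + cT = (b/7)S + (c + b/7)T. Technique versus none at equal other items is therefore c + b/7, that is, the printed HR times 18.5^(1/7) = 1.517.

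- Epidural: 3.14 × 1.517 = 4.76.
- Block: 7.55 × 1.517 = 11.45.

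The limits depend on an unreported covariance. From the printed intervals the SEs are ln(78.4/4.39)/3.92 = 0.735 for adherence (0.105 per item), 0.415 for epidural and 0.480 for block. For correlations from −1 to +1 the SE of the sum is 0.310–0.520 (epidural) and 0.375–0.585 (block).

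| | HR | Lower limit | Upper limit |
|---|---|---|---|
| Epidural | 4.8 | 1.7–2.6 | 8.7–13.2 |
| Block | 11.5 | 3.6–5.5 | 24–36 |

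No correction is computed for non-surgical complications, because the adherence OR is not printed, or for pain, because the text must first be reconciled (see the fix).

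**Events per term.** Adherence plus the five named adjusters, one coefficient each, makes 6 terms: 30/6 = 5.0 surgical, 33/6 = 5.5 non-surgical, 21/6 = 3.5 readmission. Technique terms would lower these. The Cox model has about 98 discharges if both deaths were in hospital (an assumption), so 98/8 = 12 per term even with both techniques.

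**Size of the bias.** Two simulations used n = 100, assumed item frequencies and an assumed technique mix, with 6 or 8 terms.

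- With 21 or 33 events and a true log OR of −3.9 (OR 0.02), the mean maximum-likelihood estimate was −4.47 to −4.70, an inflation of 15–20%; Firth gave −3.92 to −4.02. Maximum-likelihood coverage was about 94%, type I error 4.5–6.7%, and failed fits at most about 1%.
- With 30 events, inflation was 10–15% and Firth stayed within about 4%. Of 178 fits with maximum-likelihood p between 0.02 and 0.04, none lost significance under Firth.

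**Per-item scale.** Surgical OR 0.02^(1/7) = 0.57, upper limit 0.59^(1/7) = 0.93. Discharge HR 18.5^(1/7) = 1.52 (4.39^(1/7) = 1.24 to 78.4^(1/7) = 1.86).

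**The case against.** Much can be said for the authors. The forest plots ordinarily show the fitted terms and may show the reference levels; they were not available here, so the details may be on record. The protocol gives one score definition, the reported values fit it, and RESULTS names five adjusters. A reader might infer that no term list or score version exists; that goes too far. What stands is narrower: the text omits the technique terms and their reference, and does not say whether the regional item was kept in the modelled score.

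Comparing techniques at equal total adherence is also a legitimate contrast. If epidural and block are mutually exclusive and cover all regional use, the six- and seven-item models are the same fit written differently, with the same adherence test. This stands, and it limits the overlap to a matter of interpretation.

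On sparsity, a reader might infer as few as 21/8 = 2.6 events per term. That needs both technique terms in the readmission model, whereas the text reports no technique estimate for readmission and mentions the block only for discharge. A reader might also infer that penalised estimation is required. The simulations do not show that: coverage and type I error are near nominal, and a shift from 0.02 to about 0.03 lies well inside an interval of 0.00 to 0.59. Firth fitting is justified by the bias in effect size, at least as a sensitivity analysis.

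**Conclusion.** The point holds as a minor one with a cheap improvement. A component is reported beside the composite that contains it, clearly so in the discharge model. If the seven-item score was fitted and the reference is no regional technique, the technique HRs understate technique versus none at equal other items by a factor of about 1.5. If the reference is another technique, they need no such correction. It would be wrong to conclude that the printed HRs are in error or that the adherence finding falls: directions, the adherence test (under the reparametrisation above) and the crude primary comparison are unchanged.

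Even with a six-item score the technique estimates remain associations. Most of the other items (oral intake, catheter, walking, physiotherapy, chest tube) come after surgery and may follow from analgesia.

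For the logistic models, 3.5 to 5.5 events per term at the documented minimum means that the size of the adherence odds ratio is probably overstated, by about 10–20% on the log scale under the assumed frequencies. Significance is not expected to change. The Cox model is not sparse.

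**What to change.** - For each model, state the terms and the reference category for technique in the text. Where technique terms stay, refit with a six-item score that excludes regional analgesia; otherwise drop the technique terms and keep seven items. Present technique estimates as associations.
- Add Firth-penalised logistic fits with profile-likelihood intervals, at least as a sensitivity analysis, and report events per term.
- Report adherence per item: on the printed results, surgical OR about 0.57 (upper limit 0.93) by maximum likelihood and discharge HR about 1.52 (1.24–1.86). If Firth becomes the main analysis, replace the 0.57 with the Firth value.
- Reconcile the pain statements in RESULTS. The sentence that makes adherence the sole factor for surgical complications extends to pain (Figure 2B). Epidural is then linked to pain with a citation of Figure 2A, the panel also cited for readmission.

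The cost is re-running existing models on existing data. Odds ratios should move slightly toward 1. A six-item score on a 0–1 scale changes the adherence HR by rescaling alone, 18.5^(6/7) = 12.2, with the per-item value still 1.52; a note should say so, to prevent the change being read as a weaker association.

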Implementation of an ERAS program in patients undergoing thoracic surgery at a third-level university hospital. An ambispective cohort study.

(Short title: ERAS implementation in thoracic surgery)

31/12/2019

NCT ID not yet assigned

METHODS

Study design and participants

This study analyzes the implementation of an ERAS program in a thoracic service of a third level hospital (*Hospital Fundación Jiménez Díaz, Madrid, Spain*). To this end, we designed an ambispective cohort study, with a prospective arm of patients undergoing thoracic surgery within an ERAS program versus a retrospective arm of patients before the implementation of the protocol. Our centre's ethics committee approved our study before the start of patient recruitment, January 2018 Ref: EO071-18_FJD. This study followed the Strengthening the Reporting of Observational Studies in Epidemiology ([STROBE](#)) reporting guideline for cohort studies¹³.

After informed consent, we included patients consecutively since the implementation, except those who refused the inclusion in the study or were under 18 years old. We also asked for informed consent from the patients who were part of the retrospective cohort. For the calculation of the required sample size, we assumed that the ERAS program would result in a 25% reduction in the absolute risk of suffering a surgical complication. Since the surgical complication rate for our patients in 2016 was 40%, a type-I error of 5% and a power of 80% would require 47 patients per arm.

Procedures

We recruited 50 patients throughout 2018 and 2019 and compared them with data from the last 50 patients in 2016, the year in which we knew the surgical complication rate. We followed up each patient for 30 days after surgery through hospital and primary care medical records. Demographic and comorbidity data were collected from all patients, from which we calculated Charlson's comorbidity index¹⁴ for all patients.

We designed our centre's ERAS program through different measures during the preoperative, intraoperative and postoperative period. During the preoperative period, the patients and their families received comprehensive multidisciplinary information about the protocol, as well as their daily goals and expected discharge date. Also, a team

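### The SAP tests 30-day surgical complications both by cohort and by ERAS adherence under one significance rule, and names neither the deciding test nor the family of tests behind the q-values

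*SAP*

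**What the plan says.** **Outcome and sample size.** The Protocol (Outcomes) names one primary outcome: "The primary outcome was the number of patients with 30-day surgical complications". Its components are listed there: "We defined air leakage, bleeding, infection, and reintervention as surgical complications". The sample size (Protocol, Study design and participants) is per arm, starts from a 40% complication rate in 2016, and rests on a program effect: "we assumed that the ERAS program would result in a 25% reduction in the absolute risk of suffering a surgical complication".

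**Analysis.** The SAP (Statistical analysis) compares outcomes by cohort, using the Pearson test for discrete variables. It then turns to adherence, regardless of cohort: "We performed a multivariate logistic analysis to study the association of complication rates, readmission or pain with ERAS adherence, clinical and demographic data". Significance requires p and q below .05 for every comparison, with the false discovery rate held below 5%. The text does not say which p-values enter the q-value calculation, and it calls neither analysis primary, secondary or exploratory.

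**Results.** By cohort: "We found no difference between the two groups in either surgical complications" (18/50 vs 12/50, p = 0.19). By adherence: "ERAS adherence was the only factor associated with a reduction in surgical complications" (OR 0.02, 95% CI 0.00 to 0.59, p = 0.03). The section closes by reporting that the q-value step removed no significant p-value.

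**The concern.** The title and the sample size ask whether introducing the program reduces surgical complications, and only the cohort contrast addresses that. The adherence model asks whether patients who achieved more of the seven items, in either cohort, had fewer complications. Both are legitimate questions, but the plan gives both tests equal standing on the single primary outcome.

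Three things follow.

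- A significant adherence result can be taken as evidence on the primary outcome when the powered contrast is null.
- Whether the adherence result passes the plan's own rule depends on a family of tests that is not stated.
- Adherence is partly measured after surgery. The score counts chest tube removal within 48 hours and ambulation within 24 hours, while air leakage, bleeding and reintervention are outcome components. A patient with an air leak may keep the tube longer and so score lower. Part of the association may therefore run from complication to adherence.

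**Working it through.** **1. The powered contrast.** Inputs (Protocol): 40% falling by 25 points to 15%, 5% type I error (two-sided assumed), 80% power. With unpooled variance:

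n = (1.96 + 0.8416)² × (0.40×0.60 + 0.15×0.85) / 0.25² = 7.849 × 0.3675 / 0.0625 = 46.2, so 47 per arm.

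This reproduces the stated figure, so the sample size belongs to the cohort contrast.

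**2. The cohort result.** Inputs (SAP, Results): 18/50 and 12/50.

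- Pearson, uncorrected: χ² = 100 × (18×38 − 32×12)² / (50×50×30×70) = 1.714, p = 0.190. This matches the reported 0.19.
- OR (ERAS vs standard) = (12/38)/(18/32) = 0.56. SE of log OR = √(1/12 + 1/38 + 1/18 + 1/32) = 0.443. 95% CI 0.24 to 1.34.
- Reduction in risk: 12 points (95% CI −5.8 to 29.8).

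**3. The adherence result against the q-value rule.** Benjamini-Hochberg is assumed: q(i) is the smallest value of p(j) × m / j over ranks j ≥ i, for m tests.

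| Family | Calculation for p = 0.03 | q |
|---|---|---|
| Two primary-outcome tests (0.03, 0.19) | 0.03 × 2 / 1 | 0.06 |
| Four adherence results (<0.001, 0.007, 0.01, 0.03) | 0.03 × 4 / 4 | 0.03 |
| Twelve printed outcome p-values | 0.03 × 12 / 9 | 0.04 |

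The twelve are 0.19, 0.06, 0.19, 0.03 (cohort); 0.03, 0.01, 0.007, <0.001 (adherence); 0.008, 0.03, 0.006 (epidural); and <0.001 (intercostal block). Values printed as <0.001 are entered as 0.001. The three values of 0.03 occupy ranks 7 to 9, hence the divisor of 9. The adherence result passes with the two wider families and fails with the narrowest.

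**4. Chance of a false positive on the primary outcome.** This needs the correlation between the two test statistics, which the documents do not give. It is approximated by the correlation between adherence and cohort, ignoring covariates.

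- Reported adherence: 0.29 (0.14 to 0.43) and 0.71 (0.57 to 0.82). IQR/1.349 gives SDs of 0.29/1.349 = 0.21 and 0.25/1.349 = 0.19, so about 0.20.
- Half the median gap is 0.42/2 = 0.21. Correlation = 0.21/√(0.21² + 0.20²) = 0.72.

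Under no effect, from the bivariate normal distribution:

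| Correlation | Either p < .05 suffices | Benjamini-Hochberg on the pair |
|---|---|---|
| 0.6 | 8.8% | 4.7% |
| 0.72 | 8.2% | 4.5% |
| 0.8 | 7.8% | 4.4% |

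**5. Do the two estimates conflict?** Assume adherence enters as a 0-to-1 proportion. Over the 0.42 median gap, the point estimate becomes 0.02^0.42 = 0.19 and the upper limit 0.59^0.42 = 0.80. The rescaled interval runs from near 0 to 0.80 and includes the cohort OR of 0.56.

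**The case against.** **The hierarchy is largely visible.** The sample size is per arm and assumes a program effect, the cohort comparison comes first in the SAP, and the adherence models follow as a later step. The Results report primary and secondary results by cohort, ahead of the multivariate section. This stands, and it makes the repair uncontroversial. It does not stop the adherence result from counting as significant evidence on the primary outcome under the rule as written.

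**The q-values deal with multiplicity.** In part. If the family were just the two primary-outcome tests, the error rate would stay near 4.5%. A reader might take the 8% as the plan's own error rate; the documents do not support that, because the plan requires q as well as p. But the family is unstated, and false discovery rate control does not say which test decides.

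**Stronger readings that do not hold.** A reader might infer any of the following.

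- The plan gives opposite answers, or the two results cannot describe one effect. Both estimates favour ERAS, and the rescaled intervals overlap widely (step 5). One estimate is also adjusted and the other crude.
- A positive headline has displaced a null result. The documents contain no abstract or conclusion. The null cohort result is stated plainly and first, and the adherence result is worded as an association.
- The adherence models were not pre-specified. This is not established. Adherence is a listed secondary outcome with seven defined items. The Protocol is dated 31/12/2019, at the end of recruitment, and the SAP text sits beside the results, so these documents cannot show when either analysis was chosen.

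**The cohort test is unadjusted and the cohorts differ.** This also stands: COPD was 24% vs 8% and hypertension 52% vs 30%. It is a reason to add an adjusted cohort contrast. Changing the exposure to adherence does not answer it.

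**Conclusion.** The point holds as a gap in labelling and in the definition of the q-value family, and the gap affects what may be concluded. The powered contrast gives p = 0.19 and does not show a benefit. The adherence model gives p = 0.03, with q = 0.04 or 0.06 depending on which of two plausible families is used. If either p < .05 sufficed, the false-positive chance on the primary outcome would be about 8% (7.8 to 8.8% for correlations of 0.8 to 0.6). Whatever its q, the adherence association cannot stand in for the program effect, because a complication can lower the score.

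This rests on three assumptions: Benjamini-Hochberg q-values, the correlation approximated from medians and IQRs, and adherence entered as a 0-to-1 proportion (step 5 only). Part of the SAP text, the tables and the figures were not available, so a designation there cannot be excluded.

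**What to change.** 1. State in the SAP that the cohort contrast on 30-day surgical complications is the single primary analysis and alone answers whether the program reduced complications.
2. Label the adherence models as secondary or exploratory associations, and say that this ranking was made explicit after the data were available.
3. Define the family of tests for the q-values, and keep the primary test outside it.
4. Where the Results report the adherence association with surgical complications, add that it does not show a program effect when the cohort contrast is null, and that some adherence items can be affected by a complication.
5. Report a covariate-adjusted cohort contrast beside the Pearson test as a sensitivity analysis, because the cohorts differ on COPD and hypertension.

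**Cost.** Wording plus one further model on existing data. With 18 + 12 = 30 events, the covariate set must stay small: cohort plus five covariates would leave 30/6 = 5 events per parameter. The adherence OR carries less weight, and the primary result is reported as null.
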